6.2 THE MECHANISMS OF ANTI-NOCICEPTIVE EFFECTS OF PARECOXIB

In an *in vitro* study by Mitchell *et al.* (1994), the authors, using preparations of broken cells and cyclooxygenase enzymes that had been purified, demonstrated that acetylsalicylic acid (ASA*) was only twice more potent than salicylate in terms of COX-

2 inhibition despite both having identical analgesic profile. The authors then hypothesized that the analgesic activities of both ASA and salicylate might be attributed to their predominant action on COX-2 rather than COX-1 since ASA has much superior COX-1 inhibitory action (i.e. 100 times more potent) to salicylate whilst both of them having equianalgesic capacity. Nevertheless, due to the *in vivo* nature of this experiment, the findings should be treated with caution when extrapolating and correlating the results to other *in vivo* experimental models and clinical studies.

It is a well-known fact that prostaglandin E2 (PGE₂) has the capacity to sensitize the peripheral nerve endings to pain (Warner and Mitchell 2004). This is substantiated by Svenson and Yaksh (2002) who had explicated in their excellent review article that the COX-2 enzyme could be indigenously found in the dorsal and ventral grey matter of the spine, dorsal root ganglia and even in the glial cell such as astrocytes. Apart from that, Beiche et al. (1998) also confirmed the presence of COX-2 using immunohistochemical techniques in the neurons that are located in the whole layers of spinal cord's lamina, especially in its outermost superficial layer. The presence of constitutive COX-2 in the neuronal cells of all lamina of the spinal cord may explain for the acute antinociceptive effect of the intrathecal administration of COX-2 inhibitors. Furthermore, Pinardi et al. (2005), together with the observations made Samad et al. (2001) and Seybold et al. (2001), further endorsed the conclusion drawn from the other studies that the COX-2induced prostanoid at the spinal level may result in the perpetuation of hyperalgesic state. These perhaps partly expound the abolition of hyperalgesic state induced by the substance P and the NMDA-mediated nociceptive transmission via cycloxygenase inhibition (Malmberg and Yaksh 1992) and carrageenan-induced thermal hyperalgesia by the COX-2-specific inhibitor that was intrathecally administered (Yaksh et al., 2001). In addition, Warner and Mitchell (2004) also stated that the induction of COX-2 expression and hence PGE₂ synthesis by the injured cells may in turn result in the neuronal hyperexcitability that will cause pain hypersensitivity in the neighbouring uninjured cells. Moreover, Ossipov *et al.* (2004) also established the presence of μ -opioid receptors in the same locality (i.e. the outermost laminae of the spinal cord's dorsal laminae) as COX-2 inhibitor. All these facts lend further support to the hypothesis that the combination of analgesic or anaesthetic agents with divergent mechanistic profiles may be more effective in attenuating acute pain and prolonging the effects of anaesthetic agents (Phillips and Currier 2004). The results of these prior research hence corroborated the outcomes of our study that the addition of parecoxib to other anaesthetic agents may further reduce the sensitization of nerve ending to pain and, in general, reinforce the duration of sensory and motor blockades.

Based on the findings obtained from their murine model of abdominal constriction, Abacioglu and coworkers (2000) has advocated that the components of the L-arginine / nitric oxide (NO) / cGMP cascade may be involved in the transmission of nociceptive processes both peripherally and centrally by either a direct effect on the nociceptors per se or by the involvement of other related pathways of nociceptive processes induced by NO (Abacioglu *et al.*, 2000). Nitric oxide (NO) is involed in the antinociceptive activity of morphine and the intrathecal administration of morphine modulates spinal antinociception by interacting with the NO-glutamate cascade. In contrast, the activity of COX-2 may be stimulated by NO (Dudhgaonkar *et al.*, 2004), which in turn seems to be modulated by morphine administered intrathecally. In addition, COX-2 and inducible NO synthase are both frequently and simultaneously co-regulated (Simmons *et al.*, 2004).

6.3 PARECOXIB-ASSOCIATED TOXICITY AND ADVERSE EVENTS IN BRACHIAL PLEXUS BLOCKS

It is also crucial to establish whether injecting parecoxib directly into the brachial plexus resulted in neurotoxicity. We found that no recipients of parecoxib during the brachial plexus block reported any evidence of neurotoxicity. Our findings corroborated the findings of Liu *et al.* (2013) and Kim *et al.* (2011).

Liu *et al.* (2013) followed up the patients for two months after surgery and they found out no single episode of paraesthesia was reported by the study participants. As a result, the authors believed that their study provides the first direct evidence that parecoxib can be safely tolerated when injected into the peripheral nerve or spinal cord. Besides, the neurotoxicity of parecoxib administered into the epidural space was investigated and no behavioural or histological changes attributed to the neurotoxicity in the spinal cords of rats were observed following the administration of parecoxib.

The fact that there is a low incidence of toxicity associated with parecoxib when used for brachial plexus block may popularise its use. Besides, due to its opiod-sparing effect, Kim *et al.* (2011) has recommended that parecoxib can be safely combined and administered intrathecally with other opioid such as morphine. Hence, the potentially-fatal side effects of opioids such as death, respiratory depression and thrombosis can be avoided. Apart from that, it is also worth mentioned that since parecoxib only acts on enzyme system and not on receptors, the risks of tolerance, resistance and addiction will be smaller than drugs of opioids class (Wang *et al.* 1995).

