Eighty six (n=86) subjects were randomised to either group and analysed. There were higher durations of sensory and motor blocks in the adjunct parecoxib + ropivacaine group compared to the ropivacaine-only groups (sensory block duration: 6.5 hours vs 5.0 hours, median difference = 1.5 hours, p value <0.001; motor block duration: 4.84 hours vs 3.86 hours, median difference = 0.97 hours, p value <0.001). No significant differences between the two intervention arms with respect to sensory (9 minutes vs 9 minutes, median difference = 0 minute, p value = 0.511) and motor blockades (17 minutes vs 18 minutes, median difference = 1 minute, p value = 0.832) onset. Besides, there no significant difference in terms of complete sensory and motor blockades at 30 minutes post supraclavicular block between parecoxib + ropivacaine and ropivacaine-only groups (sensory blockade at 30 minutes: 100% vs 97.7 %, p value = 1.000; motor blockade at 30 minute = 100% vs 97.7%, p value = 1.000). No adverse events were reported in both intervention arms and the trial was not ended prematurely.

Conclusion

Adjunct parecoxib significantly enhances the durations of sensory and motor blockades, but not their onset and complete sensory and motor block at 30 minutes following supraclavicular brachial plexus block.

(395 words)

SECTION ONE

INTRODUCTION

Brachial plexus block (BPB) has enjoyed ubiquitious popularity for upper limb surgeries (Raju and Coventry, 2013). It provides sufficient anaesthesia for surgical procedures involving upper limbs due to the propinquity of the brachial plexus' trunks and division when they pass the first rib (Gamo *et al.*, 2014).

There are a few common techniques for BPB and one of the most frequentlyutilised one is supraclavicular BPB (Raju and Coventry, 2013). It is not only an efficient mode of anaesthesia intraoperatively, but it is can also provide a quick-onset and dense anaesthesia for surgical procedures that involve the proximal mid-humerus down to the distal hand with excellent safety profile (Raju and Coventry, 2013; Gamo *et al.*, 2014). The supraclavicular block (SCB) is performed above the clavicle and aims at the level of the nerve trunks or division of brachial plexus (BP). Other frequently-employed alternatives include infraclavicular block, interscalene block and axillary BPB (Raju and Coventry, 2013).

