 - Motor blockade was also evaluated every 5 minutes up to 30 minutes following the completion of administration of intervention.
 - Motor block was assessed by subject's capability of flexing his / her elbow and hand against gravity. This was then graded according to the scale utilised by Borgeat, Ekatodramis and Durmont (2001).
 - Motor block success was considered achieved when the motor power was reduced to grade 3 or more based on the criteria used by Ammar and Mahmoud (2012).
- Intra-surgical assessment:
 - Requirement of block supplementation, surgical wound infiltration and patient requested sedation or general anaesthesia
 - Surgical anaesthesia success was defined as surgery without the requirements of block supplementation, general anesthesia (administered for incomplete block) or surgical site infiltration

- Haemodynamic monitoring was performed at baseline, after LA injection, after 15 min, 30 min, 1 hour of block procedure & after completing surgery.
- Postoperative assessment:
 - Sensory and motor blockade durations were assessed on half-hourly basis (up to 12 hours postoperatively), during the post surgical period.
 - Patient-controlled analgesia (PCA) morphine or IV tramadol was given as rescue analgesia.
 - Pain scores were assessed using the visual rating scale (VRS) (0-10) where pain was evaluated when the patients were resting at 1, 2, 4, 12, 24 hours postoperatively.
 - The duration of analgesia (time interval from the completion of local anesthetic administration until the first need of rescue analgesia in the form of PCA morphine or IV tramadol) and the amount of morphine or tramadol consumed during the postoperative 24 hours were also documented.
 - Any evidence of complications (e.g., bruises/swelling at the block site, chest pain/ breathing difficulty, dysaesthesia/ muscle weakness in the operated extremity not related to the site of operation) were also recorded.
 - Surgeons were alerted to report any neurological problems not related to surgery during the clinical rounds prior to the patients were discharged from the hospital.
 - Anaesthetic preferences (one of the following: 1) the BPB; 2) block under deep sedation; 3) block under GA).
 - Preferred block for future hand operations was then recorded.

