5.4 THE ADVERSE EVENTS ASSOCIATED WITH ROPIVACAINE AND / OR PARECOXIB

No subjects reported any significant and serious side effects associated with ropivacaine and parecoxib. The signs and symptoms of side effects that are commonly associated with ropivacaine administration such as CNS (seizures, peri-oral numbness, paraesthesia, dysaesthesia, tremor, dizziness) and cardiovascular toxicities (hypotension, bradycardia and arrythmias) were not reported by any study participant in both intervention groups. Besides, no significant side effects related to parecoxib administration (gastrointestinal bleeding, anaphylaxis reactions such as swelling, rash and breathing difficulties, jaundice, abnormal liver function tests etc.) were experienced by the study participants.

The trial was not stopped prematurely and lasted for the whole duration as planned.

SECTION SIX

DISCUSSION

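### Section 6.3 concludes that toxicity is low from zero reported neurotoxicity in 43 parecoxib recipients, with no interval or observation period, although rates up to 8.2% (two-sided 95% limit) remain compatible with the data

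*Combined protocol and SAP*

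**What the plan says.** Section 6.3 presents possible neurotoxicity of parecoxib injected at the brachial plexus as an important question and answers it with "We found that no recipients of parecoxib during the brachial plexus block reported any evidence of neurotoxicity". It says this agrees with two earlier studies: a randomised axillary-block trial, whose investigators "followed up the patients for two months after surgery" and reported no paraesthesia, and a rat study of epidural parecoxib. It then states "The fact that there is a low incidence of toxicity associated with parecoxib when used for brachial plexus block may popularise its use".

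The number exposed has to be found elsewhere. The Abstract says "Eighty six (n=86) subjects were randomised to either group and analysed", and Table 5.1 gives 43 per arm.

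The postoperative assessment in section 4.10.2 has three parts that bear on nerve injury:

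- Sensory and motor block were checked every half hour, up to 12 hours after surgery.
- Complications were recorded, including dysaesthesia or muscle weakness in the operated limb not explained by the operation site. No time is given for this.
- Surgeons were asked to report "any neurological problems not related to surgery during the clinical rounds prior to the patients were discharged from the hospital".

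The last postoperative assessment with a stated time is the 24-hour pain score.

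Section 5.4 reports "No subjects reported any significant and serious side effects associated with ropivacaine and parecoxib". Its list of parecoxib effects that nobody experienced includes "jaundice, abnormal liver function tests etc". The limitations in section 6.4 discuss sample size only in terms of power to reject the null hypothesis.

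**The concern.** A zero count in a small group carries little information about uncommon harms, and without an interval the reader cannot see how little. Section 6.3 moves from that count to two stronger statements: that it corroborates earlier work, and that a low incidence is a fact. The first also compares unlike observation periods. A trial that looked for paraesthesia over two months is said to be supported by one whose described surveillance ends at discharge.

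Nerve injury is the specific safety question raised by giving this drug perineurally instead of intravenously. A reader deciding whether to adopt the adjunct would weigh the gain of about 1 to 1.5 hours of block in Table 5.4 against that risk. The report as worded suggests the risk has been shown to be small.

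The liver-test entry in section 5.4 is a smaller instance of the same problem. An effect that only a laboratory test can reveal is listed as absent, while section 4.10 describes no laboratory test.

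**Working it through.** The documents give no rate, interval or safety sample size for this point, so there is no figure of theirs to reproduce.

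**Inputs**

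- Exposed to perineural parecoxib: n = 43 (Table 5.1).
- Neurotoxicity events reported among them: x = 0 (section 6.3).
- Confidence level: 95%, taken from the 0.05 significance level in section 4.13. This is an assumption, since no level is stated for safety.
- Perineural parecoxib recipients in the cited axillary-block trial: 50 (section 2.4).

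**Step 1. Upper limit for 0/43**

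- Exact (Clopper-Pearson), two-sided: 1 − 0.025^(1/43) = 0.0822, so the 95% CI is 0 to 8.2%.
- Exact, one-sided: 1 − 0.05^(1/43) = 0.0673, or 6.7%.
- Wilson, two-sided: 1.96² / (43 + 1.96²) = 0.082.
- Rule of three: 3/43 = 0.070.
- Jeffreys, two-sided: the 0.975 quantile of Beta(0.5, 43.5) = 0.056.

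Every one of these methods leaves 5% inside the interval.

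**Step 2. How often would 43 patients show nothing?**

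P(0 events) = (1 − p)^43.

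| True rate p | P(0 of 43) |
|---|---|
| 1% | 0.65 |
| 2% | 0.42 |
| 3% | 0.27 |
| 5% | 0.11 |
| 8% | 0.03 |

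A rate of 1 to 3% would usually, or quite often, go unseen. For scale, section 2.1 describes a series of 40 supraclavicular blocks in which two patients (2/40 = 5%) had postoperative complications, namely Horner's syndrome and transient paraesthesia.

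**Step 3. How many patients with no events would support a low rate?**

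For a one-sided 95% upper limit u, n = ln(0.05) / ln(1 − u), rounded up. A limit of 2% needs 149 exposed patients and a limit of 1% needs 299. The trial has 43.

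**Step 4. Does the cited trial rescue the statement?**

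Counting its 50 perineural recipients as 0/50 and adding them gives 0/93. The exact two-sided upper limit is then 1 − 0.025^(1/93) = 0.039, or 3.9%. This is illustrative only, because the block approach, the ropivacaine concentration and the observation period differ.

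**Step 5. Observation periods side by side**

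| | Cited trial (as reported in 6.3) | This trial (4.10.2) |
|---|---|---|
| Neurological observation | two months after surgery | checks to 12 hours, complication recording (timing not given), surgeon reports before discharge |
| After discharge | included, if discharge came before two months | none described in the available text |

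The two zero counts overlap only for the early period. For later events, the available text gives this trial nothing with which to corroborate the other.

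**The case against.** The strongest reply is that the quoted sentence is accurate as a report and that the observation was more than casual. Section 4.9 defines block duration as time to complete recovery of sensation in C5 to T1 and of motor function, so early neurological recovery was examined directly and its duration is reported. Dysaesthesia and weakness were also listed for recording. The low-incidence sentence follows a paragraph on the earlier trial and the rat study, so it may not rest on this trial alone. The two-month follow-up of the cited trial is openly stated. Section Seven makes no safety claim and makes its outlook depend on future studies. This reply stands to the extent that frequent early deficits are unlikely. It does not supply an interval, an observation period or a safety caveat, and adding the cited trial still leaves 3.9%.

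Several stronger readings are tempting and should not be made.

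- A reader might infer that nerve problems were sought only on ward rounds. Section 4.10.2 describes more than that.
- A reader might infer that nobody was followed after discharge and that delayed events could not be detected. The case report form breaks off in the available copy, so one can say only that no such follow-up is described.
- The same limit applies to liver tests. Section 4.10 describes none, but that does not prove none were done.
- A reader might take section 6.3 as recommending wider use. It predicts that use may spread.
- A reader might round the limit to one patient in 12. That is 8.33%, just above the limit of 8.22%.

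**Conclusion.** The point holds as a matter of reporting and interpretation. Zero of 43 supports a statement that no neurotoxicity was reported in the observed period, with an exact two-sided 95% CI of 0 to 8.2% (one-sided upper limit 6.7%). It does not support low incidence as a fact. It can corroborate a two-month result only for the early period that both trials observed.

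The 8.2% is the boundary of what the data exclude. It is not an estimated rate, and nothing in the documents suggests that parecoxib caused nerve injury.

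The result rests on three assumptions: all 43 patients received the drug perineurally and were observed throughout the period, the events are independent, and the conventional 95% level applies. If fewer than 43 were fully observed, the limit rises. The efficacy results are unaffected.

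The liver-test point holds only in a limited form: section 5.4 lists an absence for which section 4.10 describes no measurement.

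**What to change.** 1. In sections 5.4 and 6.3, report neurotoxicity in the parecoxib arm as 0/43 with its exact two-sided 95% CI of 0 to 8.2%, and state how long and by what means patients were observed.
2. In section 6.3, restrict the corroboration and low-incidence statements to events seen in that period, or replace them with a sentence saying that uncommon or delayed neurotoxicity cannot be excluded.
3. In section 6.4, add the precision of the safety data and the length of neurological observation as limitations.
4. In section 5.4, remove abnormal liver function tests from the list of absent effects unless tests were done. If they were, say when and in how many patients.

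The cost is one interval and a few revised sentences. It needs no new data and no re-analysis of efficacy.

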6.4 LIMITATIONS OF THE STUDY

The first limitation of this study is the small size employed in this trial. As a result, the power of the study might be affected, resulting in the failure of rejecting the null hypothesis. However, we have already meticulously calculated the sample size of this study based on the findings of Liu *et al.* (2013) and the total subject obtained is presumably sufficient to provide at least 90% power in rejecting the null hypothesis. Nevertheless, the effect size demonstrated by the findings Liu *et al.* (2013) may be much larger than ours and as a result, they required a much smaller sample size to confidently reject the null hypothesis. It is highly recommended that a larger sample size should be employed if future researchers would endeavour to verify our findings.

The second limitation of our study is much more subtle. It is highly recommended that the future statistical analysis of a trial data should be done within the Bayesian framework, not solely within the frequentist setting. In this trial, the use of p values as the decision rule to determine whether a null hypothesis should be rejected or not may lead to incorrect conclusion since p value on itself is not the probability of a null (or studied) hypothesis is true (Wasserstein and Lazar, 2016). P value is actually just an assertion on the compatibility of our findings (or data) are with the hypothesis prespecified before the p value is obtained and assumed to be true (Wasserstein and Lazar, 2016). Besides, p value is also not a measure of effect size since a large p value does not mean that effect size is small and clinically negligible and a small p value represents a large and clinicallyrelevant effect size (Wasserstein and Lazar, 2016). Apart from that, p value is also not a measure whether a null hypothesis should be accepted or rejected since a small p value is not indicative of an evidence against null hypothesis or vice versa. This is because there are many other competing hypotheses that may be more compatible with the data than the tested null hypothesis (Wasserstein and Lazar, 2016). In fact, a borderline p value, for instance p equals 0.049, is just a weak against the null hypothesis and is usually lumped together with any p value that is less than 0.05 (Greenland et al., 2016). As a result of this statistical fallacy associated with the misinterpretation of p value, the number of positivebut-irreproducibe findings in trials will start to rise (Halsey et al., 2015).

Another drawback of p value is we cannot incorporate the prior information obtained from the results previous trial (i.e. from Liu *et al.*, (2013)) with the findings of our study to alter our belief on the validity of tested hypotheses. Bayesian statistics provides a better tool to address the shortcomings of the frequentist school of statistics (Spiegelhalter *et al.*, 2004). In the Bayesian school of thought, the information contained in our findings is represented by the likelihood of our data and the prior information (i.e. the results obtained from Liu *et al.*, (2013)) is conveyed by the prior distribution. Our conclusion on whether to accept a statistical hypothesis will then depend on our posterior belief which is an updated prior after mathematically combining it with the likelihood of the data in this fashion:

Prior X Likelihood = Posterior

However, Bayesian statistics suffered from several drawbacks which hamper its ubiquitous use by the scientific community. The obvious disadvantage of using Bayesian statistics is, however, the intractable posterior distribution obtained which results in statistical methods that computationally intensive. To compute the posterior distribution that represents the researcher's belief after "seeing" the information in the data and integrating it with the prior belief is arduous especially for multi-dimensional cases. The only way to solve this problem is to resort to statistical simulation using the Markov Chain Monte Carlo (MCMC) method which requires a state-of-the-art computer.

The third limitation of our study is the enrollment criteria we used to screen the patients. we excluded the definite pain-related main factors (eg, psychiatric anxiety and alcohol abuse) but did not limit other factors that also might affect pain sensation (eg, age and sex). If we had stricter enrollment criteria such as restricting the study to one certain type of surgical procedure or just in females or males, the findings of our study will be more cogent. Fourthly, we also did not evaluate the pain threshold of the study

participants since we are not in possession of any valid apparatus that can establish the threshold of heat or pressure-induced pain in humans accurately. We did evaluate the preoperative VRS as a surrogate measure for the pain threshold of each study participant but we believe this is not an accurate measure of the participants' pain tolerance. Finally, we only employed a single dose of parecoxib (i.e. 20 mg parecoxib) and consequently we were not being able to evaluate the association between different doses of parecoxib and the trend in the duration and onset of sensory and motor blockade. However, we did ascertained that the inclusion of 20 mg parecoxib to ropivacaine increased the duration of motor and sensory blockades.

SECTION SEVEN

CONCLUSION

All in all, our conclusively demonstrated that the addition of parecoxib to ropivacaine prolonged the duration of sensory and motor blockades, but not their onset. Several mechanisms have been proposed that may explain the differential effects of parecoxib on both onset and duration of the blockades. Besides, we also discussed about a few limitations of our study and recommended several remedies to improve the designs and analyses of future trials addressing the same research question. Contigent upon the findings of future studies, a 20 mg adjunct parecoxib will provide better anaesthetic effects than a single 0.75% ropivacaine in patients undergoing upper limb surgeries.

REFERENCES

- Aberg G. Toxicological and local anaesthetic effects of optically active isomers of two local anaesthetic compounds. Acta Pharmacologica et Toxicologica 1972;31:273–286.

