With respect to upper limb surgery, there was similar quality of pain relief with ropivacaine and bupivacaine in a trial conducted among patients who had interscalene block prior to major open surgeries to their shoulders (Borgeat *et al.*, 2001). However, the authors observed that the hand strength returned more expeditiously and the degree of paraesthesia at the finger level was less in patients receiving 0.2% ropivacaine than in those receiving 0.15% bupivacaine (Borgeat *et al.*, 2001). At 24 hours after the performance of interscalene block, the hand strength (the primary endpoint) was reduced

by 48% in 0.2% ropivacaine recipients and 66% in bupivacaine recipients (p value <0.05) (Borgeat *et al.*, 2001). Furthermore, the hand strength was completely recovered for subjects in ropivacaine arm at 6 hours following the cessation of ropivacaine infusion. In bupivacaine group, however, there was a protracted recovery of hand strength since it was still reduced by 25% after the end of bupivacaine administration and the difference was significant when comparison was made with the ropivacaine group (Borgeat *et al.*, 2001). Nevertheless, the results of this study should be taken with a pinch of salt due to the controversial use of the non-validated bulb-grip device test as a measurement tool for motor strength by the authors.

In another study conducted locally by Mageswaran and Choy (2010), subjects undergoing elective or orthopaedic upper limb surgery were randomized into receiving either 0.5% ropivacaine or 0.5% levobupivacaine via infraclavicular brachial plexus block. The mean onset for sensory and motor block were significantly higher in 0.5% ropivacaine recipients than 0.5 levobupivacaine recipients (sensory block: 13.5 minutes vs 11.1 minutes (p value = 0.003), motor block: 19.0 minutes vs 17.1 minutes (p value = 0.013). However, no statistically-significant difference was found with regard to the analgesic efficacy at 6 hours after the surgery. Again, the findings of this study should not be taken at face value and hence careful consideration should be exercised before recognising the validty of such results since the number of participants allocated in each intervention group was small (n = 24 per group). Hence, further studies are required to gain further information on the exact benefits of ropivacaine over other anaesthetic agents such as bupivacaine for upper limb surgeries.

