4.11 SAMPLE SIZE DETERMINATION

Sample size calculation was performed using Power & Sample Size (PS®) software version 3.1.2 (Dupont and Palmer, Vanderbilt, Nashville, Tenessee, 2014) based on the following outcome parameters:

i) Motor Block Duration –based on Liu et.al, 2013

We are planning a study of a continuous response variable from independent control and experimental subjects with 1 control per experimental subject. In a previous study the response within each subject group was normally distributed with a standard deviation of 139 minutes (Liu *et al.* 2013). If the true difference in the experimental and control means of motor block time is 138 minutes and assuming the attrition (drop-out) rate was 20%, 44 subjects (22 in each intervention arm) were required to reject the null hypothesis that the population means of the experimental and control groups are equal. The type I (α) and type II (β) were fixed at 0.05 and 0.1, respectively and hence the power (1- β) of the study is 0.9.

ii) Sensory Block Duration - based on Liu et.al, 2013

We are planing a study of a continuous response variable from that required 1 control per experimental subject (1:1 control-to-experimental unit ratio). In a previous study, the response within each subject group was normally distributed with standard deviation of 140 minutes (Liu *et al.* 2013). If the true difference in the experimental and control means of sensory block time is 104 minutes and assuming the attrition (drop-out) rate is 20%, we required 39 experimental subjects and 39 control subjects to be able to reject the null hypothesis that the population means of the experimental and control groups are equal with probability (power, $1 - \beta$) of 0.9.The type 1 error probability (α) associated with this test of this null hypothesis is 0.05.

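### Section 6.4's "the total subject obtained is presumably sufficient to provide at least 90% power in rejecting the null hypothesis" is supported only for the two block durations, and not for the onset and 30-minute endpoints whose nulls were not rejected

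*Combined protocol and SAP*

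**What the plan says.** Section 4.11 contains two calculations, both for duration and both taken from one earlier axillary-block trial.

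- Motor block duration: "In a previous study the response within each subject group was normally distributed with a standard deviation of 139 minutes", with "If the true difference in the experimental and control means of motor block time is 138 minutes". The stated requirement is 22 per arm.
- Sensory block duration: "If the true difference in the experimental and control means of sensory block time is 104 minutes", with an SD of 140 minutes. The stated requirement is 39 per arm.

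Both use alpha 0.05 and power 0.9. No difference, SD or power is given for onset or for block at 30 minutes. The Abstract nevertheless lists duration, onset and the 30-minute proportions together as primary endpoints, and Section 3.4 states a null hypothesis for each.

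Section 6.4 gives small size as the first limitation, because "the power of the study might be affected, resulting in the failure of rejecting the null hypothesis". It answers that "the total subject obtained is presumably sufficient to provide at least 90% power in rejecting the null hypothesis", without naming an endpoint. It then concedes that the earlier trial's effect "may be much larger than ours and as a result, they required a much smaller sample size to confidently reject the null hypothesis", and recommends a larger sample in future work.

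Section Seven concludes that adding parecoxib "prolonged the duration of sensory and motor blockades, but not their onset". The Abstract's conclusion says the same and adds complete block at 30 minutes.

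**The concern.** The worry raised in Section 6.4 applies only to nulls that were not rejected. Tables 5.4 and 5.5 show which these are:

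| Endpoint | Sized in 4.11? | Result |
|---|---|---|
| Sensory duration | yes | p < 0.001 |
| Motor duration | yes | p < 0.001 |
| Sensory onset | no | p = 0.577 (0.511 in the Abstract) |
| Motor onset | no | p = 0.832 |
| Complete sensory block at 30 min | no | p = 1.000 |
| Complete motor block at 30 min | no | p = 1.000 |

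The power figure therefore covers exactly the endpoints where the worry did not arise. It is silent on the four where it did.

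This matters because the onset result is used as a finding in its own right. Section Seven presents it as conclusive. Section 6.1 contrasts it with the onset difference it attributes to the earlier axillary-block trial, and infers that parecoxib's effect weakens at the higher ropivacaine concentration. Both readings need some showing that the trial could have detected an onset effect, and an unqualified 90% appears to supply it.

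**Working it through.** **Reproducing Section 4.11.** n per arm = 2·SD²·(1.960 + 1.282)² / difference², two-sided alpha 0.05.

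- Motor duration: 2·139²·10.51/138² = 21.3, so 22, as stated.
- Sensory duration: 2·140²·10.51/104² = 38.1, so 39, as stated.

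These match only without the 20% dropout allowance. With 86 analysed, that does not lower the power achieved for the durations.

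**Power for the durations at 43 per arm.** Power = Φ(difference/(SD·√(2/43)) − 1.960).

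- Motor: 138/(139·0.2157) = 4.60, power 99.6% (noncentral t 99.5%).
- Sensory: 104/(140·0.2157) = 3.44, power 93.1% (noncentral t 92.6%).

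**Onset.** Table 5.4 gives IQRs of 5 and 6 minutes (motor) and 2.25 and 3 minutes (sensory). The documents give no SD, so I assume SD = IQR/1.349: 3.71 to 4.45 minutes for motor and 1.67 to 2.22 minutes for sensory. Section 5.2 finds onset non-normal, so the results are approximate.

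Difference detectable with 90% power = 3.242·SD·√(2/43), or with 43·0.955 in place of 43 for the Mann-Whitney test:

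| | Lower SD | Higher SD |
|---|---|---|
| Motor onset, t / Mann-Whitney | 2.6 / 2.7 min | 3.1 / 3.2 min |
| Sensory onset, t / Mann-Whitney | 1.2 / 1.2 min | 1.6 / 1.6 min |

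The documents offer two numerical benchmarks for motor onset:

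- Section 2.2.3, ropivacaine against levobupivacaine ("motor block: 19.0 minutes vs 17.1 minutes (p value = 0.013"): 19.0 − 17.1 = 1.9 min. Power is about 48–65% over the SD range and the two tests.
- Section 2.4, parecoxib against saline in an infraclavicular bupivacaine block: (316.24 − 120.45)/60 = 3.26 min. Power is about 91–98%.

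**Complete block at 30 minutes.** Table 5.5 reports 43/43 against 42/43. With 43/43 in one arm, Fisher's exact test gives p = 0.055 for five failures in the other arm and p = 0.026 for six, so at least six are needed; one was observed. If true success is 100% in one arm and 90% in the other, power is P(X ≥ 6) with X ~ Binomial(43, 0.10), about 26%. For 80% against 100% it is about 89%. For 97.7% against 100% it is about 0.04%.

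**The case against.** Several points on the other side are sound.

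- Section 6.4 is hedged. Small size is the first limitation listed, the power clause is qualified as a presumption, and a concession and a call for a larger trial follow. Section 6.4 also warns that a large p value does not imply a negligible effect. These points soften the tone. However, the concession still takes the duration-sizing trial as its reference, and nothing says that onset and 30-minute block were never sized.
- A reader might infer that the 90% statement is false for motor onset. The documents do not support that. Power exists only against a stated difference, and none was set. The 1.9-minute benchmark compares two local anaesthetics, in a study of 24 per group that Section 2.2.3 itself treats with caution. On the only quantified parecoxib effect on motor onset, power is above 90%, although Section 2.4 criticises that trial too.
- Sensory onset looks well served: power exceeds 99% for the 2.4-minute difference in Section 2.2.3 (13.5 − 11.1). That is a calculation after the fact, not a power the plan stated.
- The SDs are derived from IQRs of non-normal data, and Section 4.10.2 schedules assessments every 5 minutes. This is why ranges are shown.
- Once the data are in, an interval is more informative than power. For motor onset, U = 900.5 against 924.5 expected implies a shift of about 0.2 minute. With a half-width of about 1.96·4.09·0.2157 = 1.7 minutes, the outer limit is roughly 2 minutes. A reader might infer from the 48–65% power that a 2-minute effect could well have been missed; power alone does not justify saying so.

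None of this establishes 90% power for an endpoint whose null was not rejected.

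**Conclusion.** The concern holds as a matter of scope. The 90% figure is correct for the two durations (about 93% and over 99% at 43 per arm) and unsupported for sensory onset, motor onset and complete block at 30 minutes. Unsupported is the accurate word. Under the IQR-based SD assumption, motor onset is above or below 90% depending on whether the true difference exceeds about 2.6 to 3.2 minutes, and the documents do not say what difference matters. The 30-minute proportions are the starker case: with success near 100% there is little room for improvement, and even 90% against 100% has only about 26% power. The test results and p values are unaffected. What changes is how far the non-significant results can be read as evidence of no effect.

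**What to change.** In Section 6.4, limit the 90% statement to sensory and motor block duration. Add that onset and 30-minute block were not sized. Give the differences detectable with 90% power (about 2.6 to 3.2 minutes for motor onset and 1.2 to 1.6 minutes for sensory onset, with the SD assumption stated) and the roughly 26% power for 90% against 100% complete block.

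In Section Seven and the matching Abstract conclusion, replace the statement of no effect on onset with: *no difference in onset or in complete block at 30 minutes was detected*. Report a 95% confidence interval for each onset difference, for example Hodges-Lehmann, and for the difference in each 30-minute proportion. Do not assert, on power alone, that a 2-minute motor-onset effect could have been missed.

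The cost is rewording and a few intervals from data already held. The downside is a less favourable power statement.
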